12.4 Special categories, check all that apply

- Minors /Children
- Students
- Employees - Civilian
- Employees - Contractor
- Resident/trainee
- Cadets /Midshipmen
- Active Duty Military Personnel
- Wounded Warriors
- Economically Disadvantaged Persons
- Educationally Disadvantaged Persons
- Physically Challenged (Physical challenges include visual and/or auditory impairment)
- Persons with Impaired Decisional Capacity
- Prisoners
- Pregnant Women, Fetuses, and Neonates
- Non-English Speakers
- International Research involving Foreign Nationals - Headquarters Review is necessary

You must also consider the requirements of DoDI 3216.02, paragraph 7.e.

You must also consider the requirements of DoDI 3216.02, Enclosure 3, paragraph 7.e.

12.5 Inclusion Criteria:

Order Number	Criteria
1	DEERS eligible
2	Between the ages of 18-64 (inclusive) years
3	Meets the American College of Rheumatology (ACR) diagnostic criteria for knee osteoarthritis-- i.e., Knee pain AND at least three of the following criteria: 
 1. >50 years old 2. Morning stiffness <30 minutes 3. Crepitus on active movements 4. Tenderness of the bony margins of the joint 5. Bony enlargement 6. No palpable warmth
	Ability to read and understand English language for consent purposes

4	
5	Ability to commit to study intervention and follow-up
6	Willingness to avoid prohibited treatments while enrolled in the study (i.e., NSAIDs/COX-2 inhibitors and ASAs for 5 days prior to and 2 weeks following their study injection or beginning of treatment, and Oral steroids, steroid injections, and viscosupplementation are not permitted for the study duration in the treated knee).
7	Radiographic evidence of knee osteoarthritis as assessed by Kellgren-Lawrence grade 2 or higher (may be assessed during formal screening, post-consent)

12.6 Exclusion Criteria:

Order Number	Criteria
1	Current participation in other research studies for knee OA
2	Previous enrollment for contralateral knee
3	Hx of arthroscopic surgery on the study knee within the past year
4	Hx of arthroplasty on the study knee
5	Received dry needling within the past 4 weeks
6	Received prolotherapy (e.g., CSI or PRP injection), within past month
7	Recent (within the last 3 months) lower extremity injury (e.g., ankle sprain, meniscus tear or sprain, etc.) that required professional medical attention, and occurred in the ipsilateral extremity of the study knee
8	Confounding, coexisting pathology suspected to be the primary source of their pain [e.g., acute meniscal tear (with mechanical symptoms), ligamentous changes (with clinical instability) or hemarthrosis]
9	Current or chronic sciatica (lumbosacral radiculopathy) resulting in chronic or intermittent lower extremity pain, numbness, or tingling
10	Diagnosis of neuropathy affecting sensation to pain
11	Diagnosis of inflammatory arthropathy
12	Diagnosis of fibromyalgia or chronic fatigue syndrome
13	Hx of adverse reaction to a PRP injection (either documented in the medical record or shared by the patient during screening)
14	Tattoo in treatment area
15	Diagnosis of porphyria (light induced allergy) or photosensitive eczema
16	Current use of medications associated with sensitivity to heat or light (e.g., amiodarone, chlorpromazine, doxycycline, hydrochlorothiazide, nalidixic acid, naproxen, piroxicam, tetracycline, thioridazine, voriconazole)
	Current use of pacemaker

17	
18	Hx of underlying cardiac disease
19	Diagnosis of autoimmune disease
20	Albinism
21	Current pregnancy or plans to become pregnant during intervention period
22	Hx of memory problems, dementia, and/ or impaired decision-making ability
23	Any other serious medical condition(s) that might preclude optimal outcome and /or interfere with participation (e.g., intra-articular sepsis, bacteremia, fracture, joint instability, rheumatoid arthritis, osteoporosis, cancer, coagulopathy, etc.)

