Synovial fluid will be aspirated according to standard of care (SOC) guidelines. If, at the time of joint aspiration, there is a "dry tap" (i.e., no fluid is returned), the provider will lavage the joint with a standardized quantity (10ml) of sterile Normal Saline and then aspirate the lavage. There are no harmful effects from lavaging the synovial joint with sterile saline.

The synovial fluid will be labeled with a sample ID and study visit, and transported to MAMC Department of Clinic Investigation (DCI) for storage and processing. Any excess synovial fluid will be safely discarded per standard protocol. Ice will be utilized when necessary.

Synovial fluid processing and storage are outlined below in respective sections.

The research team will maintain a biospecimen sample master key that links the sample IDs to the participant study IDs. No PII/PHI will be stored with the biospecimen sample key.

Randomization:

Participants that meet final eligibility criteria will be randomized to a study arm using a computer-generated randomization model prepared by the study biostatistician, to assign participant 1:1:1:1 across all study arms (PT, PT+PRP, PT+PBMT, or PT+PRP+PBMT).

Study Intervention:

Study interventions will be documented in the participant's EMR and on the Study Treatment Documentation Log (Appendix F).

Standard of Care (SOC) Physical Therapy (PT):

All participants will complete a standard PT program addressing individual strength, mobility, and flexibility deficits in both proximal and distal muscle groups. The provider may also use other modalities to address distal issues. If a participant has not been placed on profile at the time of consent, a profile may be written by the study medical provider to ensure limitation of activities, as appropriate.

The PT treatment participants receive in this study will be standard of care; that is, the PT treatment regimen will not be standardized across study participants and/or dictated by study-specific criteria. PT treatments will be recorded on a Chart Review CRF (Appendix I).

SOC PT + Platelet-Rich Plasma (PRP):

In addition to SOC PT, participants assigned to PT+PRP group will receive PRP treatment, as outlined below.

PRP Preparation:

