The PRP will be prepared following standard technique by drawing 60cc blood from the participant through venipuncture, and spinning the blood sample in a centrifuge (for approximately 17 minutes), adjusting for leukocyte poor-platelet rich plasma (LP-PRP). This sample will be prepared by the study provider (physician assistant or physician). Any leftover blood will be safely discarded per standard protocols.

A small portion of the injectant PRP (approximately 1 cc) will be sent to MAMC DPALS for complete blood count (CBC) cytology to monitor standardization and reproducibility. This portion will be labeled by participant ID and study. De-identified hardcopy results will be obtained from MAMC DPALS, and CBC results will be reported on Appendix G (CBC Results CRF).

PRP Injection:

PRP injection procedures will follow current clinical recommendation and standard operating procedures. Prior to the injection, the area will be sterilely prepared and anesthetized with either ethyl chloride spray or lidocaine (limited to the cutaneous and subcutaneous layer, so as not to alter the synovial contents). Then, the participant will receive LP-PRP injection in the affected knee area under ultrasound guidance. Qualified study providers will inject 2-5cc LP-PRP using an 18-gauge 1/5-inch needle for both aspiration and subsequent injection. Study providers will select the injection portal they are most comfortable with, in order to achieve an accurate intra-articular injection. The PRP injection procedure is expected to take approximately one hour.

One PRP injection is sufficient to observing the necessary clinical and molecular medicine outcomes.

Post-procedural instructions will be provided in a participant handout (Appendix Q).

SOC PT + Photobiomodulation Treatment (PBMT):

In addition to SOC PT, the PBMT group will receive PBM treatment, as outlined below.

PBM treatments will occur 3 times each week, for 3 weeks. A member of the study team will measure the treatment area according to a standard protocol and calculate the treatment time (approximately 5-20 minutes). PBMT will be delivered at 6 J/cm² and 25W and applied in a serpentine pattern to the knee area. Participants will be asked to refrain from using perfumes or plant extracts (e.g., St. John's Wort) in the treatment area(s), as this can increase skin photosensitivity.

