The PBMT will be provided by a trained study team member. Training for the PBMT will be conducted by a LightForce representative. PBMT will be delivered using the LightForce® XPi 25W device with the Smart Hand Piece technology, created by LiteCure, LLC/DJO (New Castle, DE) which has a built-in accelerometer in the hand piece that controls the speed of light delivery to the treatment area. The LightForce® XPi therapy laser is an FDA cleared device for the treatment of pain. The trained team members will use the Smart Hand Piece technology, which achieves effective treatments and improves dosing accuracy by assessing the operator's speed and providing real-time visual (red – amber – green light) and sensory feedback. The Smart Hand Piece is calibrated to shut-off when moving too slowly, and warn the operator when moving too fast by vibrating. (See LightForce Brochure). The therapy is delivered through a flexible optical fiber threaded through the hand piece, which contains a rolling glass massage ball.

SOC PT + PRP + PBMT:

In addition to SOC PT, the PRP and PBMT group will receive PRP treatment (outlined above) and PBM treatment (outlined above).

Participants in this group will start PBM treatments on the same day after receiving the study PRP injection. On the day of the PRP injection, the participant will be instructed to rest for 5-10 minutes prior to the PBMT application and team member will ensure the participant is comfortable not in pain. Immediately following the study injection, the team member will take care not to provide the PBMT over the injected area; however, all subsequent PBM treatments will be delivered to the knee where the PRP was injected.

Concomitant Medications & Treatments:

Allowed Concomitant Medications:

Patients are allowed acetaminophen and usual medications.

Prohibited Treatments:

Participants will be asked to avoid NSAIDs/COX-2 inhibitors and ASAs for 5 days prior to and 2 weeks following their study injection or beginning of treatment.

Oral steroids, steroid injections, and viscos supplementation are not permitted for the study duration in the treated knee.

Follow-Up Data Collection:

Regardless of study arm assignment, all participants will be asked to log their activity, overall function rating, pain, and medication intake (Appendix E), daily, for 6 weeks. A team member will check-in with the participant weekly to collect the activity log.

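### Light-sensitising drugs are excluded at entry, but the visible NSAID restriction ends at 2 weeks while the laser course runs for 3 (minor safety point, cheap to fix)

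*Combined protocol and SAP*

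**What the plan says.** - **Entry (12.6, criterion 16).** The plan excludes "Current use of medications associated with sensitivity to heat or light (e.g., amiodarone, chlorpromazine, doxycycline, hydrochlorothiazide, nalidixic acid, naproxen, piroxicam", followed by tetracycline, thioridazine and voriconazole. The criterion concerns use at entry. It gives no look-back period and no on-study duration.
- **On-study restriction (10.1, Prohibited Treatments).** Participants are to "avoid NSAIDs/COX-2 inhibitors and ASAs for 5 days prior to and 2 weeks following their study injection or beginning of treatment". Inclusion criterion 6 (12.5) repeats this window in a list introduced by i.e., which reads as complete. The PRP aftercare note in 18.2 also gives 2 weeks for NSAIDs and COX-2 inhibitors.
- **Allowed medication (10.1).** "Patients are allowed acetaminophen and usual medications".
- **Laser schedule (10.1).** "PBM treatments will occur 3 times each week, for 3 weeks". For the combination arm: "Participants in this group will start PBM treatments on the same day after receiving the study PRP injection".
- **Other photosensitivity instruction (10.1).** PBMT participants are asked not to use perfumes or plant extracts on the treated area, because these can make the skin more light-sensitive.
- **General safeguards.** Medication intake is logged daily for 6 weeks, and "A team member will check-in with the participant weekly to collect the activity log". On the device, "The Smart Hand Piece is calibrated to shut-off when moving too slowly". Section 14.2 has PBMT changed or halted if warmth becomes uncomfortable, and sets up a study laser safety programme under a clinical laser safety officer. Sections 13.6 and 15.1 allow a participant to be removed for safety.

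**The concern.** Naproxen and piroxicam are treated as reasons not to receive the laser at all, yet the one on-study rule that covers them expires while sessions are still being given. Elsewhere the plan does carry rules through treatment: steroids and viscosupplementation are barred for the whole study, criterion 21 covers pregnancy plans over the intervention period, and the perfume instruction applies during PBMT because of photosensitivity. The same care is not visibly applied to the listed drugs.

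The situation is foreseeable. Section 9.2 names oral pain relievers among the usual treatments for knee OA, and a 2-week stop date gives a natural moment to restart one. What is at stake is an avoidable chance of skin heating or erythema in someone who restarts or newly starts a listed drug during the laser course. No endpoint, significance level or power calculation depends on it.

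**Working it through.** The plan states no figure for this overlap, so there is nothing to reproduce. The check is a count of sessions against the restriction window.

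**Inputs.** Three sessions a week for 3 weeks (10.1). A restriction of 2 weeks, taken as 14 days, from the injection or beginning of treatment (10.1, 12.5). First laser session on the injection day in the combination arm (10.1), so day 0 is the same for both clocks. Up to 200 participants, 50 per arm (11.2, 11.4).

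**Step 1, total sessions.** 3 × 3 = 9.

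**Step 2, fixed weekly pattern.** Let sessions fall on days 0, a and b of each week, with 1 ≤ a < b ≤ 6. There are C(6,2) = 15 such patterns. Week 3 sessions fall on days 14, 14 + a and 14 + b.
- Strictly after day 14: 2 of 9 (22%) in all 15 patterns.
- On or after day 14: 3 of 9 (33%) in all 15 patterns.
- Last session: day 14 + b, that is day 16 to day 20. A Monday/Wednesday/Friday course starting on a Monday has sessions on days 14, 16 and 18.

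**Step 3, sensitivity to placement.**
- Any three distinct days within days 14 to 20: C(7,3) = 35 placements. Those that include day 14 number C(6,2) = 15 and leave 2 sessions after day 14. The other C(6,3) = 20 leave 3.
- Calendar weeks, weekdays only, Wednesday start: week 3 covers days 12 to 16, giving C(5,3) = 10 placements. Sessions after day 14 number 0 in one placement, 1 in six and 2 in three.

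So 2 to 3 of 9 is the usual result, and an uneven calendar-week schedule can give fewer.

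**Step 4, drugs covered.** Criterion 16 names 10 drugs. Two are NSAIDs and fall under the 2-week restriction. The remaining 10 − 2 = 8 have no explicit on-study rule.

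**Step 5, people concerned.** The point applies to two arms, so at most 2 × 50 = 100 of 200 enrolled. Within those arms it concerns only people who restart or newly start a listed drug. The plan does not say how many that would be.

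**Step 6, after the fix.** With the restriction tied to the last delivered session, 0 of 9 sessions fall outside it.

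**The case against.** The strongest objection is that the point rests on what is absent from text we cannot fully see. A per-session medication check would naturally sit in the treatment log (Appendix F), the participant handout (Appendix Q), the laser training plan (Appendix T), the consent form, or the clinical laser safety officer's programme described in 14.2. None of that content is available here, and its absence is not a gap in the plan. This stands: the sponsor may only need to confirm that a check exists and align the protocol wording. What remains is that the stated NSAID window, repeated in three sections, ends before the laser course does.

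It can also be said that contact is close. A trained team member delivers every session, medication is logged, and treatment responds to uncomfortable warmth. Section 14.1 describes heating and erythema as very rare. This keeps the absolute risk low. Even so, none of these measures is a stated medication rule, and the warmth rule acts only once warmth is felt.

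Two stronger readings are tempting and should not be drawn.
- A reader might infer that the plan permits naproxen in week 3. It does not say so. Expiry of the window suggests it, but a drug that bars entry is not clearly one of the participant's usual medications. For newly started non-NSAID drugs such as doxycycline the text is silent or ambiguous.
- A reader might infer a much larger overlap in the PT+PBMT arm, on the view that the clock could start with physical therapy before the first laser session. The documents give no such lag. Section 10.1 says "the PT treatment regimen will not be standardized across study participants", which concerns the content of therapy and not when it begins.

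**Conclusion.** The mismatch is real and minor. In the combination arm, on a fixed weekly pattern, 2 of 9 laser sessions fall after the NSAID restriction ends, or 3 of 9 if day 14 itself is unrestricted, and no visible text then bars restarting naproxen or piroxicam. The same count holds in PT+PBMT if the beginning of treatment means the first laser session, which the plan does not define.

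The result assumes a 14-day window, the same weekdays each week and no rescheduled sessions. It counts calendar days and does not estimate exposure or harm. Few participants are likely to be affected. The point is an optional improvement and no obstacle to the trial.

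**What to change.** In 10.1 (Prohibited Treatments) and inclusion criterion 6, ask participants assigned to either PBMT arm to avoid naproxen, piroxicam and the other criterion 16 drugs until after their last delivered PBMT session. Tie the rule to the last delivered session, because 10.1 provides for missed appointments to be rescheduled. Ask about new medications at each PBMT visit. If a listed drug is medically needed, it is given, and the study physician decides whether to defer or omit the remaining sessions. Other NSAIDs may resume at 2 weeks as now, and the two arms without PBMT are unchanged. If the laser safety programme or an appendix already holds such a check, a cross-reference in 10.1 is enough.

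**Cost.** One sentence in two places and one question at each of the 9 visits. An occasional session will be deferred or omitted, and a deferred one could fall after the 3-week questionnaires. Participants in the PBMT arms go about one more week without two named NSAIDs, longer if sessions slip. That makes permitted NSAID choice differ slightly between arms, including the PRP versus PRP+PBMT comparison of Aim 1. The existing daily medication log will record the difference.

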13.0 Recruitment and Consent

13.1 Please describe the recruitment process, including how subjects will be identified and selected for the study.

Please see Study Procedures Section 10.1

Potential participants will be identified via four methods:

1. Under the provisions of an approved Partial HIPAA Waiver Application for this study, local study team members will review medical records of patients coming in to the Sports Medicine, Physical Therapy, Orthopedic, Podiatry, and Physical Medicine & Rehabilitation (PM&R) clinics for suspected/confirmed knee OA in order to identify prospective research participants and to seek their authorization to participate/use their protected health information for this research study. The study team will receive approval from the potential participant's provider prior to approaching for possible study participation.
2. Direct referral from local healthcare providers in the local Sports Medicine, Family Medicine, Orthopedic and Podiatry, Physical Therapy, Holistic Health and Fitness (H2F), and Physical Medicine & Rehabilitation (PM&R) clinics.
3. Patients may self-refer to participate in the study. Interested potential participants will be able to contact a member of the study team via phone or email. Potential participants who contact the study team directly will be instructed to seek care with Orthopaedics, Sports Medicine, PM&R, or their primary care manager for a physical exam for a diagnosis of knee OA, if they do not already have a diagnosis.
4. Study advertisements will be posted within the following locations, and copies will be provided to clinic staff:
 - Internal Medicine
 - Aviation Medicine
 - H2F
 - McChord Clinic
 - Winder Clinic
 - Okubo Soldier-Centered Medical Home
 - Allen Soldier-Centered Medical Home
 - Soldier Recovery Unit
 - Puyallup Community Medical Home
 - South Sound Community Medical Home
 - Armed Forces Wellness Center
 - Intrepid Spirit Center
 - Madigan Medical Mall
 - Pharmacy waiting areas, if possible
 - Physical Therapy
 - Podiatry
 - Sports Medicine
 - Tactical Human Optimization, Rapid Rehabilitation and Reconditioning (THOR3)
 - Physical Medicine and Rehabilitation
 - Coffee bar

- Dining Facility entrance
- Intranet screen saver page
- 2/75 Ranger Clinic

The local research team will keep a separate electronic screening log containing DoD ID number, ineligible/eligible, and date screened. This log will be password protected and stored in a secure folder on a secure drive accessible only by authorized local research staff. This log is needed to avoid any duplicative screening of those that are screen failures. This reduces burden on potential participants, providers, and study team and ensures the study team will not screen the same person twice or examine records for eligibility criteria when screen status is already established.

Recruitment and consent conversations will take place in a private setting (e.g., closed clinic room, investigator's office, etc.) to minimize the potential opportunity to be overheard or inadvertently witnessed.

13.2 Compensation for Participation:

Participants may receive up to \$150 for their participation in this research.

There are three opportunities to receive compensation:

- (1) when a participant completes the baseline blood draw - \$50,
- (2) when a participant turns in the completed daily activity log at the 3-week follow-up visit - \$50, and
- (3) when a participant completes the 6-week follow-up blood draw - \$50.

Participants will receive payment in the form of a gift card or Visa-type card equivalent.

Participants will only be paid for applicable research activities that they complete. They will not receive compensation for research activities they do not complete.

In accordance with the DoDI 3216.02, all human subjects (including federal employees both on and off-duty) participating in DoD-conducted or supported research may be compensated up to \$50 for each blood draw. Additionally, DHA-AI 3200.01 indicates active-duty service members may receive additional compensation for the completion of a daily health diary when completed off-duty. In accordance with DHA-AI 3200.01 the following definitions of on-duty and off-duty will apply to active duty-service member study participants:

- An individual is on-duty when they are expected or required to perform the duties of their assigned job or position.
- An individual is off-duty if the individual is not scheduled to perform any work that may arise during the period.

In order to receive compensation for the completion of the daily activity log in this research, a study team member will ask the participant to confirm that they completed the daily activity log while off-duty/on leave. It will be the responsibility of the study participant to provide accurate information regarding their duty/leave status at the appropriate compensation interval.

Upon request, the PI and/or authorized study team member may provide certification for intermittent leave, or leave on a reduced leave schedule, for planned study medical treatment(s) (in accordance with US Code Title 5, Section 6383).

13.3 Please describe the pre-screening process. If no pre-screening, enter Not Applicable in the text editor

This study has two screening phases: 1) Pre-screening based on initial inclusion/exclusion criteria (before informed consent) and 2) a formal screening phase to determine eligibility for randomization to intervention arm (after informed consent).

Pre-Screening (before consent):

If a potential participant expresses interest in learning more about the research study, a member of the research staff will briefly introduce the study, express the voluntary nature of

participation, assess interest in participating, and screen the potential participant for initial eligibility in close collaboration with the patient's attending provider. Pre-screening conversations may also take place over the phone using the Screening Script (Appendix N).

Initial eligibility (see Protocol Sections 12.5 *Inclusion Criteria* & 12.6 *Exclusion Criteria*) will be confirmed in-person using an Inclusion/Exclusion CRF (Appendix A). This Inclusion/Exclusion CRF does not record any PII/PHI.

Individuals that do not meet inclusion/exclusion criteria will be encouraged to continue to seek care with their primary care provider.

If the potential participant meets eligibility criteria as determined by the Inclusion/Exclusion CRF and expresses interest in participating in the study, an authorized study team member will initiate the formal consent discussion and, if applicable, obtain informed consent. See protocol section 13.4 for additional information on the consent process.

Formal Screening (post-consent):

As part of the formal screening procedures, all consented participants that are biological females of child-bearing age and capacity will be required to complete a urine hCG pregnancy test. If the pregnancy test is positive, per the inclusion/exclusion criteria, the participant will be formally withdrawn from the study at this point, and will be encouraged to seek care with their primary care physician. If the pregnancy test is negative, the participant will be eligible to be randomized to a study arm and continue with the study procedures.

As part of the formal screening procedures, consented participants' final eligibility status will be confirmed via X-ray. If imaging was completed within one month prior to study enrollment, the previous images may be utilized. If diagnostic images are required, imaging will be ordered by an authorized medical provider. The results of the diagnostic images will determine if the participant meets final eligibility criteria (Kellgren-Lawrence grade 2 or higher, which demonstrates possible narrowing of the joint space with definite osteophyte formation), and should continue with the study intervention.

13.4 Consent Process: Revised Common Rule, Section 219.116: General requirements for informed consent, whether written or oral, are set forth in this paragraph and apply to consent obtained in accordance with the requirements set forth in paragraphs (b) through (d) of this section. Broad consent may be obtained in lieu of informed consent obtained in accordance with paragraphs (b) and (c) of this section only with respect to the storage, maintenance, and secondary research uses of identifiable private information and identifiable biospecimens.

Are you requesting a waiver or alteration of informed consent?

Yes No

Please explain the consent process:

Consent will be obtained in accordance with principles of Belmont Report and Common Rule guidelines.

The consent form will describe the purpose of the study, the procedures to be followed, and the risks and benefits of participation. A copy of the signed consent form will be given to the participant and the original will be stored in a locked cabinet inside of a locked office. Documentation of consent will be recorded in the participant's medical record. No Legally Authorized Representatives will be utilized.

Formal consent, as represented by the act of signing a dated, IRB approved consent statement for the study will only occur after confirming eligibility using the Inclusion/Exclusion CRF, a thorough review of what is involved in the study, and after all questions have been answered.

Potential participants will be provided information regarding all available study treatments and reminded of the expectations placed on them if they enroll, including the randomization process.

The potential participant will be given a copy of the informed consent document to read before, during, and/or after discussion of the informed consent with the Research Coordinator (RC), Principal Investigator (PI), Associate Investigator (AI), or other authorized study team member. Sufficient time will be given to the potential participant to understand the study purpose, study procedures, time commitments, potential risks and benefits, and the types of health information

that will be accessed, collected, and used by the research team if they agree to participate in the study.

Questions can be raised by the potential participant at any time during the consent discussion and at any time during the conduct of the study. The potential participant will be instructed that their participation is completely voluntary and that they may withdraw from the study at any time without penalty. Their decision to participate or to not participate, or to withdraw from the study after consent, will not affect their access to health care that they are otherwise entitled to and it will not affect their military position.

The authorized study team member present during the consent conversation will confirm that the potential participant has no additional questions before deciding to provide consent.

Every effort will be made to eliminate the perception of authority, which is a particularly important consideration when recruiting active-duty study participants. When applicable, the study investigators will be in scrubs or civilian clothes instead of uniform and will introduce themselves as doctor rather than their military rank. Some potential participants may be patients of the study PI or AI. In these cases, the consent conversation will be initiated by non-physician study staff to prevent any misconception of coercion or undue influence.

Informed consent and HIPAA authorization will be obtained in person.

In the event that there are significant new findings regarding the therapy that may affect participants' willingness to continue in the study, an information sheet will be provided to all current and past participants. The informed consent document will be amended for future participants.

Following completion of informed consent, the results of the Inclusion/Exclusion CRF will be entered into REDCap, an encrypted, access controlled, password protected electronic data capture and management system housed on a DoD server and maintained by the Uniformed Services University Information Technology (USU IT), and a unique study ID will be generated. This coded study ID will be used on all research data collection forms in place of the participant's name, Department of Defense (DoD) ID, or other protected identifier. No PII will be entered into REDCap.

Please see Appendix R for additional information on REDCap.

13.5 DoDI 3216.02 requires an ombudsman to be present during recruitment briefings when research involves greater than minimal risk and recruitment of Service members occurs in a group setting. If applicable, you may nominate an individual to serve as the ombudsman.

- N/A
- Propose ombudsman

13.6 Withdrawal from Study Participation:

Explain the process for withdrawal and specify whether or not the subjects will be given the opportunity to withdraw their data their data/specimens in the event they wish to withdraw from the study

Participant Withdrawal:

Participants may withdraw from the study at any time without penalty. Participants will be informed that withdrawal will not affect their access to health care that they are otherwise entitled to and it will not affect their military position.

If a participant withdraws from the study, we may retain and analyze all coded/de-identified data collected up to the time of withdrawal if the data is necessary to maintain the integrity of the study. However, no further data will be collected after the date of withdrawal.

Participants may contact the study research coordinator/assistant or Principal Investigator to formally withdraw from the study. Participants will be advised to follow-up with their personal physician if they choose to withdraw.

Withdrawal Without Participant Consent:

A participant may be withdrawn from the study without their consent if remaining in the study might be dangerous or harmful to them. Participation may also be stopped if the military mission requires it, if they lose their right to receive medical care at a military hospital, if the study is canceled, if they fail to adhere to the protocol and/or therapy plan, or if they display inappropriate behavior towards study personnel.

